Pre-operative condition and patients outcomes will be assessed using standardized and validated measures. The primary endpoint of a mRS score will be obtained at least 90 days following treatment and again at 1 year following treatment. NIHSS score will be obtained in the emergency room before the treatment, within 24 h of treatment, and before discharge. The person who will obtain the NIHSS will be certified to obtain it. Adequacy of revascularization will be assessed at the end of treatment by the treating physician according the modified thrombolysis in cerebral infarction (mTICI) scale (see Appendix). All of these measures are standards for care and trials of acute ischemic stroke. [8-10] All case report forms will be maintained by the primary investigator at the local site, and stored within locked cabinets. The personal identifying information on the case report forms will be deidentified and assigned a code before being transferred to Akron General Medical Center for transfer of the data to a de-identified database which will be used for analysis.

IV. DATA COLLECTION

Version: 6.0

A. How and what data will be collected

Data related to patient demographics, stroke risk factors, condition prior to treatment, time of treatment, and outcomes will be collected for each patient. Data on demographics will include sex, age, and race. Data on stroke risk factors will include history of hypertension, blood pressure, prior heart attack, arrhythmias, diabetes, glucose (sugar) level at admission, and obesity. Data on condition prior to treatment will include NIHSS score determined in the emergency room. Data on time of treatment will include time from symptoms to arrival at emergency room, time to start of DCA, and time to end of the procedure. Data on outcomes will include mRS at 3 months, mRS at 1 year, NIHSS score within 24 hours and at discharge, and complications brain edema and intra-cranial hemorrhage. Other parameters within these categories could be acquired as deemed necessary for analysis of the data.

V. DATA ANALYSIS

A. Sample Size Considerations

Phase I

A power analysis has been performed based on the previous retrospective analyses of the relationship between outcomes and the CIS for phase I. The sample size was calculated for the influence of the combination of CIS and revascularization on good outcomes (mRS \leq 2) based on the following assumptions.

- The percentage of patients with fCIS will be 60%

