- A. parenchymal hemorrhage type 2 symptomatic or asymptomatic hemorrhagic transformation within the vascular territory of the index ischemic stroke within 24 hours of treatment
- B. Any neurological worsening (NIHSS increase of 4 points or more) within 24 hours of treatment.

The rate of complications will be assessed by the safety committee after evaluation of 20, 30 and 40 patients. The trial will be stopped for safety if the rate of brain edema and intracranial hemorrhage is significantly larger for the pCIS group than the fCIS group.

The safety committee will meet at the end of phase I and give its recommendation to launch phase two or not depending on their review. The primary reason not to launch phase II would be higher than expected good outcomes for the pCIS patients treated with EVT plus standard of care, giving the indication that IAT should not be withheld from patients during phase II. During phase II, the safety committee will review the data on complications as noted above and percentage of good outcomes after 10 and 20 subjects are evaluated for comparisons between the two treatment groups.

VII. STUDY LIMITATIONS

A. Potential Limitations of Procedures

The primary limitation for phase II is the small sample size. Due to the expected relatively low rates of good outcomes for pCIS patients regardless of type of treatment, the power will not be sufficient to establish whether or not treatment with IAT is beneficial for patients with pCIS. The study will, however, provide the preliminary data needed to plan for a future, larger prospective clinical trial. Potential limitations for the genetic component of this study include DNA damage due to improper handling or storage of blood samples. The Paxgene DNA tubes are designed to stabilize DNA in the blood. However, the tubes will only function properly if the instructions for inverting the tube multiple times and prompt shipment for storage at Akron General are followed.

VIII. ETHICAL CONSIDERATIONS

A. Informed Consent

Enrollment of patients will be performed in an imaging suite at each institution. Once eligibility is determined by the treating physician based on imaging, the consent process will be initiated by a study research coordinator or study nurse. These investigators are familiar with all aspects of the proposed treatment methods and typical outcomes and maintaining confidentiality of data obtained from subjects enrolled in research projects.

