- 16. Khatri P, Yeatts SD, Mazighi M, Broderick JP, Liebeskind DS, Demchuk AM, et al. Time to angiographic reperfusion and clinical outcome after acute ischaemic stroke: an analysis of

Version: 6.0

data from the Interventional Management of Stroke (IMS III) phase 3 trial. The Lancet Neurology. 2014; 13:567-74.

Version: 6.0

XI. APPENDICES

MODIFIED RANKING SCORE

SCORE	DESCRIPTION
0	No symptoms at all
1	No significant disability despite symptoms; able to carry out all usual duties and activities
2	Slight disability; unable to carry out all previous activities, but able to look after own affairs without assistance
3	Moderate disability; requiring some help, but able to walk without assistance
4	Moderately severe disability; unable to walk without assistance and unable to attend to own bodily needs without assistance
5	Severe disability; bedridden, incontinent and requiring constant nursing care and attention
6	Dead

Modified thrombolysis in cerebral infarction (mTICI) scale

- 0: No perfusion
- 1: Perfusion past the initial obstruction but limited distal branch filling with little or slow distal perfusion
- 2a: Perfusion of less than half of the vascular distribution of the occluded artery
- 2b: Perfusion of half or greater of the vascular distribution of the occluded artery
- 3: Full perfusion with filling of all distal branches

Version: 6.0 Date: 03/30/2018

Integrated Acute Stroke Flowsheet National Institutes of Health Stroke Scale

Complete a full assessment TID during the first 72 hours after admission for stroke, with any decline in neurological status, and when the patient is received from ER, ICU, or PACU into 6NW or 6 Observation. After the 72 hour period, a full assessment should be completed with any changes in neurological status, and prior to discharge.

Complete a modified assessment (the shaded sections, and any other area of concern) when the neurological assessment is required more often than TID.

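### Safety item B covers the full 24 hours after treatment, but the plan requires only one NIHSS at an unset hour in that window, so later worsening need not reach the trial data or the safety committee

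*Combined protocol and SAP*

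**What the plan says.** Section VI.A lists two complications by name for the safety committee. The second, item B, is "Any neurological worsening (NIHSS increase of 4 points or more) within 24 hours of treatment". It names neither the baseline score nor the scores from which the rise is to be read.

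Section III.D sets the study's NIHSS schedule: "NIHSS score will be obtained in the emergency room before the treatment, within 24 h of treatment, and before discharge". Section IV.A repeats it in the list of outcome data: "NIHSS score within 24 hours and at discharge". Neither gives an hour for the post-treatment score. IV.A adds an open clause: "Other parameters within these categories could be acquired as deemed necessary for analysis of the data".

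The NIHSS flowsheet in the appendices has a denser schedule: "Complete a full assessment TID during the first 72 hours after admission for stroke, with any decline in neurological status". The same instruction also calls for a full assessment "when the patient is received from ER, ICU, or PACU into 6NW or 6 Observation".

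On use, VI.A states: "The rate of complications will be assessed by the safety committee after evaluation of 20, 30 and 40 patients". Phase II reviews return to the same complications after 10 and 20 subjects. The stopping rule rests on other events: "The trial will be stopped for safety if the rate of brain edema and intracranial hemorrhage is significantly larger for the pCIS group" than for the fCIS group.

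**The concern.** Item B asks whether a rise of 4 points occurred at any time in a 24-hour window. One score at an unspecified hour answers only whether the patient was worse at that moment. A site that scores the patient an hour or two after the procedure has met III.D and IV.A in full, and a decline that evening has no required route into the study data.

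Item B is the only named complication that picks up clinical decline without a parenchymal hemorrhage. Phase II is meant to give pilot safety data on whether IAT may harm pCIS patients, in only 30 patients, so a few unrecorded events could change the picture. If scoring hours differ between the up to 6 centers, event rates will differ between centers for reasons unrelated to safety. Because no clock time is collected for the NIHSS, this could be neither seen nor adjusted for afterwards.

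**Working it through.** The documents give no expected rate of worsening and no detection rate, so there is no plan figure to reproduce. The check is mainly textual.

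**Step 1: what item B needs against what is collected**

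- *Event (VI.A):* a rise of 4 or more at any time from 0 to 24 h after treatment.
- *Scores required (III.D, IV.A):* one before treatment, one at an unset hour up to 24 h, one before discharge. Only the middle one must fall inside the window.
- *Clock times (IV.A):* symptom onset to arrival, start of DCA and end of procedure. The hour of the NIHSS is not listed.
- *Other routes:* the complications listed in IV.A are brain edema and intracranial hemorrhage. None of the eight adverse events in VIII.C is neurological worsening as such. The open clause in IV.A permits further data but requires none.
- *Flowsheet (XI):* three scores a day for 72 hours and one at any decline, timed from admission. No section sends these scores to the case report form.

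So the listed data cannot reliably supply the event that the committee is asked to review.

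**Step 2: how much could be lost (illustration only)**

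Assumptions, none from the documents: worsening starts at a time W uniform on 0 to 24 h and then persists. A single score at hour t sees the event when W ≤ t, so the share captured is t/24.

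| Hour of the single score | Share captured |
|---|---|
| 2 h | 2/24 = 8% |
| 6 h | 6/24 = 25% |
| 12 h | 12/24 = 50% |
| 18 h | 18/24 = 75% |
| 24 h | 24/24 = 100% |

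If the scoring hour is itself uniform, its mean is 12 h and the average share is 12/24 = 50%. Scores every 8 hours from a random starting point put the last score before 24 h at 16 h plus a uniform 0 to 8 h, on average 20 h, so 20/24 = 83%. Simulation with 400,000 draws gave 0.500 and 0.833. Scores triggered by a noticed decline would raise the 83% towards 100%, provided that they reach the trial data.

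**Step 3: sensitivity to the model**

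If most worsening starts early, a single score captures more than t/24. If worsening is transient, even a score at 24 h can miss it, and only a score taken at the time of decline will show it.

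**The case against.** The strongest reply is that item B defines an event, while III.D schedules routine outcome scores. Nothing confines item B to the scheduled score, and a site could report a decline from the chart. This stands to a degree. A reader might infer that the plan computes item B from one score and counts later worsening as none. The documents say neither. They only fail to require any other source, and permission to collect more data is not a requirement.

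A reader might also infer that the flowsheet contradicts III.D. It need not. It is timed from admission, names particular wards, and is not stated to apply at every center. A care form and a study schedule may differ. Where it is used, a noticed decline should be scored and charted, which narrows the gap to whether that score is carried into the trial data.

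Two further objections limit the impact. The stopping rule does not use item B, and the stated primary reason not to launch Phase II is better than expected outcomes in pCIS patients. The list holding item B is also introduced as non-exhaustive, so the committee's review is not confined to two events. Both points stand.

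Finally, nothing suggests that scoring hours would differ between fCIS and pCIS patients in Phase I, where treatment is identical. That stands too. In Phase II a difference is possible, since only one arm undergoes a procedure that typically lasts 2 to 3 hours, but it is not shown.

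**Conclusion.** The point holds as a gap between an event defined over 24 hours and data that need sample that window only once, at an unset and unrecorded hour. It is more than missing detail, because a fully compliant site can leave later worsening out of the trial data.

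The size of the loss is unknown. Under uniform onset and sustained worsening it runs from 92% missed (score at 2 h; 100% minus 8%) to none missed (score at 24 h). It would be tempting to say that half of all events are lost, but that figure needs a uniformly random scoring hour as well, which the documents do not support. With no event rate in the documents, the shares cannot be turned into patient counts.

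The consequence is weaker information for the committee's reviews in both phases, not a failure of the written stopping rule. The change is worth making because it is cheap.

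**What to change.** - **III.D and IV.A:** take the already required post-treatment NIHSS at 24 hours, within a stated window, at every center, and record its clock time. Also record, with its time, any NIHSS charted because of a decline before then.
- **VI.A:** define item B as a rise of 4 or more from the pre-treatment emergency-room NIHSS, at the 24-hour score or at any decline-triggered score up to 24 hours. Say what starts the 24-hour clock, since Phase II patients assigned to no IAT have no end-of-procedure time.
- **Reporting:** give the committee the count from the 24-hour score separately. A count over all charted scores rises with the number of scores taken, so only the fixed-time count compares centers on an equal footing.

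Under the sustained-onset model the 24-hour score captures every event. The decline-triggered scores cover transient worsening, which that model leaves out.

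The cost is a few form fields and short wording changes in three sections. Centers that do not use the flowsheet must arrange a 24-hour score. Brief fluctuations that trigger a score will count as events, which is consistent with item B covering any worsening.

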- a. Lengthen the time window of treatment for patients with fCIS from 6 hours to 24 hours. In doing so, we will offer useful treatment to patients who would otherwise be denied treatment under current standards.
- b. Encourage focusing on achieving good revascularization rather than limiting time during IAT for patients with fCIS.
- c. Improve the percentage of good outcomes in the treated population
- d. Save patients with pCIS from complications due to brain edema and intra-cranial hemorrhage that could potentially result from IAT
- e. Save the health care system the costs of futile treatment of patients with pCIS.

III. METHODS

A. Study Design:

Version: 6.0

The current study focuses on patients with acute ischemic stroke due to a blockage of the intracranial internal carotid artery or middle cerebral artery (M1). The study will be performed prospectively in up to 6 stroke centers. Akron General Medical Center is the primary institution for development of the study and data analysis for this multicenter trial. To participate in the study, all centers need to meet certain qualified requirements which include:

- One neurointerventionalist with 6 years' experience in performing IAT with multiple devices.
- Demonstrate coverage of the comprehensive stroke center 24 hours a day. The proposed study will be carried out over a period of 4 years from the initial approval date. Informed consent will be obtained for each patient, as described in section VIII. The study will be carried out in 2 phases (Figure 1).

Phase I will compare outcomes between treated patients with fCIS and pCIS. All eligible patients will be assessed by a full diagnostic cerebral angiogram with dye injection of all potential collaterals. DCA will be used to characterize the CIS. Treatment will be identical for both groups. All patients will be treated with the combination of IAT and the normal standard of care for a patient not receiving IAT (which may include IVT, but not always). The sample size will be set to have 60 patients complete the trial. Distribution of fCIS and pCIS patients will not be forced, but the option to balance groups may be employed if the percentage for one group reaches 70%.

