The population for the study will be patients with anterior circulation acute ischemic stroke due to blockage of the intracranial internal carotid artery or middle cerebral artery (M1) within 8 hours of onset of symptoms. Typically, IAT is only offered to patients up to 6 hours, with no treatment options directly targeting the clot available after that time. Occlusion of one of these vessels will be determined based on CT angiography, magnetic resonance angiography, or DCA. Only patients 18 or over will be considered for the study. Other inclusion criteria include a score of 8 or greater on the National Institute of Health Stroke Scale (NIHSS, see appendix). Exclusion criteria will include contra-indication for IAT found on initial CT, intracranial hemorrhage, stroke mimics (tumor, herpetic encephalitis, etc.), more than 1/3 hypodensity on non-enhanced head CT prior to intervention, ASPECT Score < 6, and pre-existing disability defined as mRS ≥ 2. Pregnant women will also be excluded.

[figure not shown]

Figure 1: Study design for Phase I

Version: 6.0 5

[figure not shown]

Figure 2: Study design for Phase II

C. Assessment of Resources

The multicenter study will be carried out at up to 6 stroke centers. Each center is expected to have approximately 1 patient per month eligible for the study. Enrollment of patients will be performed at the end of imaging at each institution. At Akron General Medical Center, consent will be obtained within the DCA imaging suite. Consent will be obtained by a person qualified by the local IRB other than the treating physician. At Akron General, consent will be acquired by one of two neurointerventional lab nurses. One of these two nurses is required to be present for treatment of each patient with acute ischemic stroke, regardless of participation in a study. These nurses are familiar with all aspects of the proposed treatment methods and typical outcomes. The nurses will perform documented training on methods for obtaining consent and maintaining confidentiality of data obtained from subjects enrolled in research projects.

D. Study Procedures

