- The percentage of patients with good revascularization will be 50%
- The rate of good outcomes for the combination of fCIS and good revascularization is assumed to be 70%
- The rate of good outcomes for the combination of fCIS and poor revascularization is assumed to be 20%
- The rate of good outcomes for the combination of pCIS and good revascularization is assumed to be 20%
- The rate of good outcomes for the combination of pCIS and poor revascularization is assumed to be 10%

The assumptions provide the following power analysis:

- $\alpha = 0.05$ for overall analysis and set to 0.025 for subgroup analysis comparing fCIS and good revascularization to all other groups due to multiple comparisons
- power = 0.90
- Needed Sample size = 54 patients
- An additional 6 patients completing the trial are budgeted due to risk of errors in estimated outcomes. An additional 15-20 patients are expected to be enrolled due to patients lost to the 90 day follow up and/or deviations from the protocol.

Phase II

Phase II will be an exploratory study evaluating the rates for good outcomes for patients with pCIS treated with IVT plus IAT vs. IVT (or other standard of care) only. The rate of good outcomes is expected to be approximately 13% for the IAT group with revascularization. The investigators have no prior data on expected rates of good outcomes for patients with pCIS treated with IVT only. The best possible outcome rate would be on

Version: 6.0

the order of 25% noted previously for untreated acute ischemic stroke. Due to the low levels of good outcomes, the investigators acknowledge the study will be underpowered to detect a difference between the two treatment groups for a total sample size of 30. Phase II will serve as a pilot study to initially establish estimates of rates of good outcomes for pCIS patients treated with IVT only for design of a larger prospective study.

Genetic Analysis

Genetic analysis will be performed based on the following:

- Genetic and expression analysis for the two groups based on their collateral score
- Adjust groups for cardiovascular/stroke risk factor presence and other known confounding conditions
- High density SNP array analysis will be performed for common and rare alleles
 against known collateral-related genes that have been identified in mice. These
 include human RABEP2 and its isoform RABEP1 and related gene pathways;
 VEGFA, FLK1 and their related gene pathways; NOTCH, DLL4, ADAM10,

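### Phase I schedules no complication comparison between poor and favourable CIS after 40 patients, although 75-80 are expected to be enrolled

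*Combined protocol and SAP*

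**What the plan says.** Section VI.A (Data and Safety Monitoring Plan) sets the Phase I schedule: "The rate of complications will be assessed by the safety committee after evaluation of 20, 30 and 40 patients". The sentence after it is the stopping rule: the trial stops if brain edema and intracranial hemorrhage are significantly more frequent in pCIS than in fCIS. The next meeting named in that section is the one that closes the phase: "The safety committee will meet at the end of phase I and give its recommendation to launch phase two or not". Phase II then has its own reviews, after 10 and 20 subjects.

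Section III.A gives the size of Phase I: "The sample size will be set to have 60 patients complete the trial". Section V.A builds up to that figure ("Needed Sample size = 54 patients", then "An additional 6 patients completing the trial are budgeted due to risk of errors in estimated outcomes") and adds an allowance: "An additional 15-20 patients are expected to be enrolled due to patients lost to the 90 day follow up and/or deviations from the protocol". Section III.C gives the pace, for up to 6 centres: "Each center is expected to have approximately 1 patient per month eligible for the study".

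Two other provisions bear on safety after patient 40. Section VI.A opens with a general statement that a safety committee monitors the data. Section VIII.C provides that a centre with two or more listed events has its technique evaluated by the principal investigator and the safety committee, and may be dropped.

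**The concern.** Every Phase I patient receives intra-arterial treatment (IAT). Section VIII.B records the investigators' view that IAT carries a risk in pCIS patients, through edema, hemorrhagic transformation and possibly herniation. The stopping rule exists to detect that harm, and it rests on comparing pCIS with fCIS.

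The three scheduled comparisons fall while the groups are small. At the assumed 60% fCIS, the first sets about 8 pCIS against 12 fCIS patients and the last about 16 against 24. No further comparison is scheduled as the groups grow towards their final size. If IAT does harm pCIS patients, the chance to see it and act during Phase I depends on someone deciding to look outside the schedule. The end-of-phase meeting can withhold Phase II, but it cannot protect Phase I patients already treated.

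**Working it through.** **1. The plan's own sample size.** Section V.A assumes 60% fCIS, 50% good revascularization, and good-outcome rates of 70%, 20%, 20% and 10% in the four combinations, with 90% power and alpha "set to 0.025 for subgroup analysis comparing fCIS and good revascularization to all other groups due to multiple comparisons". The fCIS group with good revascularization is 0.6 × 0.5 = 30% of patients. The rate in the other 70% is (0.3 × 0.20 + 0.2 × 0.20 + 0.2 × 0.10) / 0.7 = 0.1714. A two-sided comparison of 0.70 with 0.1714, with continuity correction and 30:70 allocation, needs 16 patients in the smaller group. 16 / 0.30 = 53.3, rounded up to 54, which matches the plan.

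**2. Expected enrolment.** 54 + 6 = 60 completers. 60 + 15 = 75 and 60 + 20 = 80 enrolled.

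**3. Patients after the last scheduled comparison.**
- Of 75 enrolled: 75 − 40 = 35, and 35/75 = 46.7%.
- Of 80 enrolled: 80 − 40 = 40, and 40/80 = 50.0%.
- Completers only: 60 − 40 = 20, and 20/60 = 33.3%.
- If a patient counts as evaluated only on completing the 90-day visit: 40 × 75/60 = 50 to 40 × 80/60 = 53 are enrolled at the third look. That leaves 25-27 (33%), before allowing for patients already treated but awaiting follow-up.

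The enrolled count is the natural denominator. Both complications listed in VI.A are measured within 24 hours, so a patient lost before day 90 is still at risk and still assessable. Edema, named in the stopping rule, has no stated time window.

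**4. Duration.** At the maximum of 6 patients a month, 35/6 = 5.8 to 40/6 = 6.7 months, and longer with fewer centres.

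**5. What further looks would add.** The documents give no complication rates and no test for the rule, so both are assumptions here. The calculation is exact and cumulative. It stops when pCIS is worse with two-sided Fisher p<0.05, at pCIS/fCIS sizes of 8/12, 12/18, 16/24 (looks at 20, 30, 40) and 20/30, 24/36, 28/42 (looks at 50, 60, 70).

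| Assumed rate, pCIS vs fCIS | Stopped by 40 | Stopped by 70 |
|---|---|---|
| 40% vs 10% | 59.7% | 85.5% |
| 30% vs 10% | 35.1% | 58.6% |
| 25% vs 5% | 39.8% | 67.7% |
| 20% vs 10% | 13.4% | 24.4% |
| 15% vs 10% | 6.1% | 11.4% |
| 10% vs 10% | 1.9% | 3.5% |
| 20% vs 20% | 3.2% | 5.0% |

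The last two rows are false stops. They rise by 1.6 and 1.8 percentage points.

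**The case against.** A reader might infer that the stopping rule is switched off at 40 patients, or that about half of Phase I runs without oversight. The documents support neither. The stopping sentence stands on its own and is not confined to the three looks, so the committee could apply it later. The general monitoring statement has no end date, and neither does the centre trigger. The trigger in fact becomes more active as patients accumulate. Take a pooled rate of 0.4 × 30% + 0.6 × 10% = 18%, assume six equal centres, and assume that these complications count as listed events. A centre's chance of two or more events is then about 30-37% at 6-7 patients and 71% at 13.

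This limits the point but does not answer it. The centre trigger examines technique at one site and does not compare pCIS with fCIS across sites. The general statement sets no time at which that comparison is made.

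Three further objections have weight. First, about half is the upper reading; on completers it is a third. Second, the large gains in the table depend on assumed excesses of 20-30 percentage points. For excesses of 5-10 points the rule usually misses the difference with or without more looks. Third, the rule is itself loosely drawn. It names no test or threshold, and it turns on edema and hemorrhage, whereas the complications listed for review are hemorrhagic transformation and neurological worsening. More looks do not repair that.

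Front-loaded looks in a small single-treatment phase can be a deliberate choice, but the protocol gives no reason for ending them at 40.

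**Conclusion.** The point holds as a gap in the schedule. After 40 patients no pCIS-versus-fCIS complication comparison is specified until Phase I is over. The gap covers 35-40 of 75-80 expected enrolments (47-50%), or 20 of 60 completers (33%). The shares rest on the plan's enrolment figures; the benefit of further looks rests on assumed complication rates, 60% fCIS and an assumed Fisher test. Under those assumptions the gain in the chance of stopping is about 24-28 percentage points for excesses of 20-30 points, and about 5-11 points for excesses of 5-10 points. It is a cheap improvement to safety oversight that should be made. It does not show that Phase I is unmonitored or that the stopping rule lapses.

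**What to change.** Amend the schedule sentence in VI.A so that the committee reviews the pCIS-versus-fCIS complication comparison after 20, 30 and 40 patients and after every further 10 enrolled (50, 60, 70) until Phase I enrolment closes. State that all treated patients count, not only completers, and that the existing stopping rule applies at each look. This leaves 75 − 70 = 5 to 80 − 70 = 10 patients after the last scheduled look.

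The cost is about three more reviews of a short table by the existing committee, and about 2 percentage points more false-stop risk under the assumed test. Treatment, sample size and data collection do not change. The undefined significance criterion and the mismatch between the rule's events and the listed complications need separate attention.
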